3.4 SECONDARY ENDPOINTS

Table 7: Secondary Objectives and Associated Endpoints

Phase 2 Secondary Objectives Phase 2 Secondary Endpoints	
1. Evaluate the safety and tolerability of INO-4800 administered by ID	1a. Incidence of solicited and unsolicited injection site reactions
injection followed immediately by EP	1b. Incidence of solicited and unsolicited systemic adverse events (AEs) by system organ class (SOC), preferred term (PT), severity and relationship to investigational product
	1c. Incidence of serious adverse events (SAEs)
	1d. Incidence of adverse events of special interest (AESIs)
Phase 3 Secondary Objectives	Phase 3 Secondary Endpoints
1. Evaluate the safety and tolerability of INO-4800	 Incidence of solicited and unsolicited injection site reactions
	1b. Incidence of solicited and unsolicited systemic adverse events (AEs) by system organ class (SOC), preferred term (PT), severity and relationship to investigational product
	1c. Incidence of serious adverse events (SAEs)
	1d. Incidence of adverse events of special interest (AESIs)
	1e. Incidence of all-cause mortality
2. Evaluate efficacy of INO-4800 in the prevention of COVID-19 disease according to degrees of disease severity in subjects who are SARS-	2a. Incidence of non-severe COVID-19 disease in SARS-CoV-2 seronegative subjects starting 14 days after completion of the 2-dose regimen until EOS
CoV-2 seronegative at baseline	2b. Incidence of severe COVID-19 disease in SARS- CoV-2 seronegative subjects starting 14 days after completion of the 2-dose regimen until EOS

		2c. Incidence of deaths due to COVID-19 in SARS- CoV-2 seronegative subjects starting 14 days after completion of the 2-dose regimen until EOS
3.	Evaluate the cellular and humoral immune response to INO-4800	3a. Antigen-specific cellular immune response measured by IFN-gamma ELISpot
		3b. Neutralizing antibody response measured by a pseudovirus-based neutralization assay
4.	Evaluate the efficacy of INO-4800 in the prevention of COVID-19 disease in subjects who are SARS- CoV-2 seropositive at baseline	 Incidence of virologically-confirmed COVID-19 disease starting 14 days after completion of the 2-dose regimen until 12 months post-dose 2 (End of Study (EOS)) in subjects who are SARS- CoV-2 seropositive at baseline

3.5 **EXPLORATORY OBJECTIVE**

See Table 8.

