3.8 SAFETY ASSESSMENT

Subjects will be followed for safety during the trial through scheduled clinic visits and phone calls. AEs, regardless of relationship to study drug, will be collected from the time of consent until 28 days post-dose 2 (i.e., Day 56). SAEs, MAAEs and AESIs will be collected from time of consent until EOS. SAEs, AESIs, and treatment-related AEs will be followed to resolution or stabilization. For the Phase 2 segment and at selected sites in the Phase 3 segment, solicited local and systemic AEs will be collected for 7 days following each dose using a participant diary.

Subjects will also be monitored for COVID-19 disease.

Please refer to the Schedule of Events (Table 3 and Table 4) for safety assessments to be performed.

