7.4 SERIOUS ADVERSE EVENTS (SAEs)

An SAE is any untoward medical occurrence that at any dose:

- Results in death;
- Is life-threatening;
 - Refers to an event in which the subject was at risk of death at the time of the event. It does not refer to an event which hypothetically might have caused death if it were more severe
- Requires inpatient hospitalization or prolongation of existing hospitalization;
 - Includes any hospitalization in which the subject has been admitted to the hospital regardless the length of stay, even if the hospitalization is only a precautionary measure to allow continued observation. However, hospitalization (including hospitalization for an elective procedure) for a pre-existing condition that has not worsened, does not constitute an SAE
- Results in persistent or significant disability/incapacity;
 - A substantial disruption of a person's ability to conduct normal life functions (i.e., the adverse event resulted in a significant, persistent or permanent change, impairment, damage or disruption in the subject's body function/structure, physical activities and/or quality of life)
- Results in congenital anomaly or birth defect and/or;
- An important medical event.
 - An event that may not be immediately life-threatening or result in death or hospitalization but may jeopardize the subject or may require intervention to prevent one of the other outcomes listed above. Examples of such events are intensive treatment in an emergency room or at home for allergic bronchospasm, blood dyscrasias or convulsions that do not result in hospitalization, or development of drug dependency or drug abuse

Clarification of Serious Adverse Events (SAEs)

- Death itself is not an AE. Death is an outcome of an AE, but when the cause of death has not been provided, use the event term: death of unknown cause;
- Confirmed COVID-19 disease that requires hospitalization is recorded on the Suspected COVID-19 Clinical Event CRF, and not recorded as an SAE;
- COVID-19 disease with an outcome of death is recorded on the Suspected COVID-19 Clinical Event CRF, and not recorded as an SAE;
- The subject may not have been receiving an investigational medicinal product at the occurrence of the event;
- Complications associated with COVID-19 disease that occur or prolong hospitalization are recorded on the Suspected COVID-19 Clinical Event CRF;

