8.5.3 SAFETY ANALYSES

8.5.3.1 Adverse Events

All AEs including injection-site reactions will be summarized among the Safety Population by frequency per treatment arm. These frequencies will be presented overall and separately by dose, and will depict overall, by system organ class and by preferred term, the percentage of subjects affected. Additional frequencies will be presented with respect to maximum severity and to strongest relationship to Study Treatment. Multiple occurrences of the same AE will be counted only once following a worst-case approach with respect to severity and relationship to Study Treatment. All serious AEs will also be summarized as above.

The main summary of safety data will be based on events occurring within 30 days of any dose. For this summary, the frequency of preferred term events will be compared between study arms with risk differences and 95% confidence intervals, using the method of Miettinen and Nurminen. As this analysis will use many event categories, and produce many confidence intervals, caution should be exercised when interpreting these confidence intervals. Separate summaries will be based on events occurring within 7 days of any dose and regardless of when they occurred.

The analyses listed above will be performed according to the Phase of the trial. For the Phase 2 segment, the analyses listed above will also be performed according to prior receipt of any non-study prophylactic COVID-19 vaccine. For the Phase 3 segment, the analyses listed above will also be performed according to SARS-CoV-2 serostatus at baseline.

For AE data, partial start dates will be imputed to the date of treatment to conservatively report the event as treatment-emergent, whenever the portion of the date is consistent

INO-4800	COVID19-311
Inovio Pharmaceuticals, Inc.	Clinical Protocol

with that of the study treatment. Otherwise, it will be imputed to the earliest date consistent with the partial date. A completely missing onset date will be imputed as the day of treatment. Partial stop dates will be assumed to be the latest possible day consistent with the partial date. AE duration will be calculated as (Stop Date – Start Date) + 1.

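### Section 8.5.3.1 plans no between-arm estimate for any SAE, any AESI or all-cause mortality over the period in which they are collected

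*Protocol*

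**What the plan says.** Section 8.5.3.1 opens with by-arm frequencies: "All AEs including injection-site reactions will be summarized among the Safety Population by frequency per treatment arm". These are to be shown overall, by system organ class and by preferred term, with further breakdowns by severity and relationship. The same layout applies to serious events: "All serious AEs will also be summarized as above".

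The section then sets the window: "The main summary of safety data will be based on events occurring within 30 days of any dose". The next sentence gives the comparison, by the method of Miettinen and Nurminen: "For this summary, the frequency of preferred term events will be compared between study arms with risk differences and 95% confidence intervals". Other windows follow, with no estimate attached: "Separate summaries will be based on events occurring within 7 days of any dose and regardless of when they occurred".

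Collection runs longer. Section 3.8 says: "SAEs, MAAEs and AESIs will be collected from time of consent until EOS". Table 7 in Section 3.4 lists SAEs as Phase 3 secondary endpoint 1c, AESIs as 1d ("1d. Incidence of adverse events of special interest (AESIs") and all-cause mortality as 1e. Section 7.4 adds a recording rule: "COVID-19 disease with an outcome of death is recorded on the Suspected COVID-19 Clinical Event CRF, and not recorded as an SAE". Section 8.1 states that the formal statistical analysis plan is contained in Section 8 itself.

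**The concern.** Following SAEs and AESIs for about 13 months serves to detect harms that are rare or late. The one planned estimate with an interval stops at about Day 58 and is computed one preferred term at a time. That suits reactogenicity and general AEs, whose collection ends at Day 56. It does not suit endpoints 1c to 1e.

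The three endpoints are affected differently:

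- **1c, SAEs.** By-arm counts over all follow-up are planned. A risk difference for any SAE is not, in any window.
- **1d, AESIs.** No table is organised by AESI status. Appendix A lists concepts such as pneumonitis/pneumonia, encephalitis/myelitis and vasculitides, which span several preferred terms. The proportion of subjects with any AESI cannot be obtained by adding preferred-term rows, because a subject with two terms would be counted twice.
- **1e, all-cause mortality.** Section 8.5.3 names no output. The SAE tables cannot supply it, because COVID-19 deaths are not SAEs.

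A late imbalance in 1d or 1e would have to be assembled by analyses chosen after the data are seen.

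**Working it through.** **1. Share of follow-up covered by the estimate.** The plan states no figure for this, so there is none to reproduce. Inputs: doses on Day 0 and Day 28 ±3 (Section 5.2), a 30-day window (Section 8.5.3.1), and last visit on Day 393 ±5 (Table 4).

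- The windows Day 0–30 and Day 28–58 overlap, so together they end at Day 28 + 30 = 58.
- Inside: 58/393 = 14.8% (59/394 = 15.0% if Day 0 is counted). Outside: 85.2%.
- Over the visit windows, the share outside runs from 1 − 61/388 = 84.3% to 1 − 55/398 = 86.2%.

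**2. What is planned for each endpoint.**

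| Endpoint | By-arm frequency, all follow-up | Risk difference with CI, all follow-up | Risk difference with CI, 30 days |
|---|---|---|---|
| 1c SAEs | Yes: overall, SOC, PT | No | Single PTs only |
| 1d AESIs as a group | No | No | No |
| 1e all-cause mortality | No | No | No |

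COVID-19 deaths are analysed separately as efficacy endpoint 2c, with a 95% CI (Section 8.5.2.1). That endpoint covers seronegative subjects from 14 days after dose 2. It does not include other causes of death, seropositive subjects or, in its definition, earlier deaths.

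**3. Illustration of what the interval is worth.** The protocol gives no SAE, AESI or death rates, so the rates here are assumptions. Arm sizes come from Table 2: 4476 + 268 = 4744 vaccine and 2238 + 134 = 2372 placebo. Events are taken as evenly spread over follow-up with a constant relative risk, so the window holds 14.8% of them. At placebo risk 0.5% and relative risk 2.5:

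- All follow-up: 4744 × 0.0125 = 59 v 2372 × 0.005 = 12 events.
- Window: 59.3 × 0.148 = 9 v 11.9 × 0.148 = 2 events.

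The criterion is that the Miettinen-Nurminen 95% CI lies above zero, which is z > 1.96 with z = (x₁/n₁ − x₂/n₂) / √[p̄(1 − p̄)(1/n₁ + 1/n₂)·N/(N − 1)], p̄ = (x₁ + x₂)/N and N = 7116. Summing the binomial probabilities of the pairs (x₁, x₂) that meet it gives:

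| Placebo risk to Day 393 | Relative risk | All follow-up | Day 0–58 |
|---|---|---|---|
| 0.5% | 2.5 | about 90% | 17% |
| 1% | 2 | 91% | 20% |
| 0.5% | 2 | 61% | 9% |
| 0.5% | 1.5 | 22% | 3% |

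The window column applies to all events pooled. Splitting by preferred term would lower it. Other settings for all follow-up: 41% at 1% and relative risk 1.5, 26% at 0.2% and relative risk 2, and 13% at 0.1% and relative risk 2.

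**The case against.** A reader might infer that the arms are not compared at all after Day 58. The documents do not support that. The same paragraph plans by-arm frequencies without a time limit, with overall and organ-class rows, and repeats the layout for SAEs. Endpoint 1c can therefore be read, and with known denominators an interval for any SAE follows from the printed counts. What is missing there is the stated estimate, not the data.

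A reader might also infer that deaths go uncompared. That too is stronger than the text allows. COVID-19 deaths in seronegative subjects are compared to end of study as endpoint 2c, and other deaths enter the SAE tables as outcomes. The gap is the all-cause total.

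Three further objections have weight:

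- Safety carries no hypothesis, and the DSMB reviews unblinded SAEs and AESIs during the trial (Section 12.1). Both are true, but monitoring is not a planned final analysis, and an estimate with an interval needs no hypothesis.
- Table detail is commonly left to a separate analysis plan. That defence is weak here, because Section 8.1 places the formal plan in these sections, and because the text does specify a comparison, with a window and unit that do not fit endpoints 1c to 1e.
- For really rare harms or small relative risks, a full-follow-up interval would usually miss the signal too. This stands, as the lower settings in the working show. The case for the change is that the endpoints need an estimate, not that power would be high.

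**Conclusion.** The point holds in limited form. Endpoints 1c, 1d and 1e have no between-arm estimate with a confidence interval over the period in which they are collected. For 1d as a group and for 1e, no summary is named at all. The only such estimate covers about 15% of follow-up, one preferred term at a time. That share follows from the protocol's own schedule and is firm.

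The power contrast is illustrative. It rests on assumed rates, an even spread of events and a constant relative risk, none of which the protocol supports or contradicts.

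The statistical section is visible in Versions 1.0USA and 2.0USA only. The material at hand also carries a Version 7.0 reference list without its Section 8, so whether the gap persists there cannot be settled here. This is worth correcting, but it does not threaten the primary analysis.

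**What to change.** In Section 8.5.3.1, add the Miettinen-Nurminen risk difference with 95% CI, from first dose to end of study (or to unblinding and crossover, if earlier), for:

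1. any SAE;
2. any AESI, as one group defined by Appendix A;
3. all-cause mortality, counting deaths from every record, including the Suspected COVID-19 Clinical Event CRF.

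Keep the 30-day preferred-term table as it is. MAAEs are not a listed endpoint, so an estimate for them is optional.

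The cost is a short text change and a few tables from data already collected, using a method already named. The downside is a few more confidence intervals, which the section's existing caution on interpreting many intervals already covers. If a later protocol version is in force, check its Section 8.5.3.1 first.

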8.5.3.2 Vital Signs

Measurements for vital signs as well as changes from baseline will be summarized with descriptive statistics: mean, standard deviation, minimum, median, and maximum values by time point and treatment arm, for the Safety population. Baseline is defined as the last measurement prior to the first treatment administration. These summaries will be performed according to Phase. For the Phase 2 segment, the analyses listed above will also be performed according to prior receipt of any non-study prophylactic COVID-19 vaccine. For the Phase 3 segment, the analyses listed above will also be performed according to SARS-CoV-2 serostatus at baseline.

8.5.4 **DISPOSITION**

Disposition will be summarized by treatment arm for the ITT population and will include the number and percentage randomized, the number and percentage who received each dose and the number who completed the trial. The number and percentage of subjects who discontinued will be summarized overall and by reason. The number in each analysis population will also be presented. These summaries will be performed according to Phase. For the Phase 3 segment, the analyses listed above will also be performed according to SARS-CoV-2 serostatus at baseline.

8.5.5 DEMOGRAPHIC AND OTHER BASELINE CHARACTERISTICS

8.5.5.1 Demographics

Demographic data will be summarized with descriptive statistics: mean standard deviation, minimum, median, and maximum values for continuous variables, and percentages for categorical variables, by treatment arm, for the ITT and PP populations. These summaries will be performed according to Phase. For the Phase 3 segment, the analyses listed above will also be performed according to SARS-CoV-2 serostatus at baseline.

8.5.5.2 Prior Medications

Prior medications are those that were used before the start of the trial (prior to Day 0). Partial stop dates of prior medications will be assumed to be the latest possible date consistent with the partial date; start dates will not be imputed. Data for all prior medications will be summarized with percentages by treatment arm, for the ITT and PP populations. These summaries will be performed according to Phase. For the Phase 3 segment, the analyses listed above will also be performed according to SARS-CoV-2 serostatus at baseline.

8.5.6 INTERIM ANALYSES

For safety issues, the DSMB could recommend stopping enrollment at any time; no formal interim analysis will be performed for this purpose. The two-sided type I error of 0.05 will not be adjusted for possible early stopping due to this aspect.

For the Phase 2 segment, group-level unblinded summaries of the immunogenicity and safety data will be produced once Week 6 visit immunology data and Week 8 visit safety

INO-4800	COVID19-311
Inovio Pharmaceuticals, Inc.	Clinical Protocol

data are complete for all subjects who have not discontinued, while maintaining subjectlevel blinding. Long-term follow-up data will continue to be collected for all subjects who have not discontinued with remaining visits through the final visit. These summaries will allow the Sponsor to have results for the purposes of dose selection for the Phase 3 portion. No subject-level immunogenicity data will be produced, and subject-level immunogenicity data will not be available in the clinical trial database until all other clinical trial data are finalized at the end of the trial. No safety summary will be provided if the total number of subjects who experience the event of interest is greater than 0 and the count of the number of subjects with the event in a given treatment group relative to the total produces a percentage less than 3%, for a given summary. The group-level unblinded production of the summaries will not include anyone directly involved with the trial or any additional unblinded personnel; only the external Contract Research Organization (CRO), ICON, which will already be providing unblinded summaries for the Data Safety Monitoring Board, will be utilized. Thus, the trial will remain blinded to the Sponsor with respect to subject treatment assignment.

8.5.7 MULTIPLICITY

There is one primary hypothesis that will be tested. As there are two interim analyses of the primary endpoint, the type I error rate will be controlled at two-sided 0.05 by using the Lan-DeMets O'Brien-Fleming approximate alpha-spending function (see Section 8.5.6).

8.5.8 MISSING VALUES

Missing data will not be imputed.

For the ITT analyses of efficacy in the Phase 3 segment, subjects with missing or unevaluable data regarding case definition will be considered cases (failures).

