This segment of the trial is case-driven. Among seronegative subjects, a total of 149 observed cases will be required for 90% power to declare the vaccine efficacious (>30%), assuming a true efficacy of 60%. A sample size of 6714 seronegative subjects is expected to be required to achieve the 149 cases assuming an underlying attack rate of 3.7%. The actual sample size may differ if the observed attack rate is different than projected. There are two formal interim analyses of efficacy; one when 50% of the cases accrue and one when 75% of the cases accrue. If the prespecified criteria for efficacy are met at either interim analysis, then enrollment will continue until 4500 subjects have been enrolled, and blinded follow-up will continue until at least those 4500 subjects have a minimum of 6 months of safety follow-up. At that point, the trial would be unblinded and placeborecipients will be offered the active product.

The primary efficacy endpoint window will begin 14 days post-dose 2 and will end at 12 months post-dose 2. All Phase 3 segment subjects will be followed for 56 weeks from the Day 0 dosing [i.e., Week 56 will be the planned End of Study (EOS) visit for this segment of the trial].

External Committee Reviews

For both the Phase 2 and 3 segments, the Data Safety Monitoring Board (DSMB) will convene regularly to review all available unblinded safety data, and additionally upon completion of the Week 8 phone call visit for all subjects enrolled during the Phase 2 segment. For the Phase 3 segment, the DSMB will also review efficacy in an unblinded fashion. Additionally, for Phase 3, an independent, blinded Endpoint Adjudication Committee (EAC) will review and confirm COVID-19 cases.

Details of each committee's scope will be provided in the respective charters.

3.1 **PRIMARY OBJECTIVES**

See Table 6.

3.2 **PRIMARY ENDPOINTS**

Table 6: Primary Objectives and Associated Endpoints

Phase 2 Primary Objective	Phase 2 Primary Endpoints
1. Evaluate the cellular and humoral immune response to INO-4800	1a. Antigen-specific cellular immune response measured by IFN-gamma ELISpot assay
administered by ID injection followed immediately by EP	1b. Neutralizing antibody response measured by a pseudovirus-based neutralization assay
Phase 3 Primary Objective	Phase 3 Associated Primary Endpoint

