8.1 STATISTICAL AND ANALYTICAL PLAN

The formal Statistical Analysis Plan is contained in the sections that follow.

8.2 **GENERAL CONSIDERATIONS**

The statistical analysis of the data will be performed by Inovio Pharmaceuticals or its representative.

This is an operationally seamless Phase 2/3 trial. The subjects and data from Phase 2 are independent from that of Phase 3.

Phase 2 Segment: This is a four-arm, multi-center, placebo-controlled, blinded, and randomized clinical trial in subjects at high risk of SARS-CoV-2 exposure. The trial's primary endpoints are antigen-specific cellular immune response measured by IFN-gamma ELISpot and neutralizing antibody responses. Secondary efficacy endpoints are safety measures. Exploratory endpoints are antigen-specific cellular immune response measured by flow cytometry and other T and B cell measures.

Phase 3 Segment: This is a two-arm, multi-center, placebo-controlled, double-blinded, and randomized clinical trial in subjects at high risk of SARS-CoV-2 exposure. The study's

INO-4800	COVID19-311
Inovio Pharmaceuticals, Inc.	Clinical Protocol

primary endpoint is the incidence of virologically-confirmed COVID-19 disease in subjects who are SARS-CoV-2 seronegative at baseline starting 14 days after completion of the 2-dose regimen until 12 months post-dose 2. The primary hypothesis is that INO-4800 will be efficacious relative to placebo (relative efficacy > 30%). Secondary efficacy analyses involve non-severe cases, severe cases, cases resulting in death, and cases among baseline SARS-CoV-2 seropositive subjects. Other secondary analyses concern safety and cellular and neutralizing antibody response. Exploratory analyses concern efficacy against variants, efficacy against asymptomatic infection, and binding antibody and cellular immunological measures.

8.3 **STATISTICAL HYPOTHESES**

Phase 2 Segment: This is an estimation segment pertaining to immunogenicity and safety. There are no hypotheses.

Phase 3 Segment: The primary hypothesis of relative efficacy greater than 30% among baseline SARS-CoV-2 seronegative subjects will be tested with H₀: $p \ge .70/(.70+k)$ vs. H₁: p < .70/(.70+k), where p is the true proportion of subjects with disease who receive INO-4800 relative to the total number of subjects with disease, and k is the total amount of follow-up time in the placebo group divided by the total amount of follow-up time in the INO-4800 group. There are no other formal hypotheses.

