This methodology is based on the following. Assuming that the number of subjects who are cases in the INO-4800 group follows a Poisson distribution with parameter λ_v and the number of subjects who are cases in the placebo group follows a Poisson distribution with parameter λ_c , then conditional on total number of subjects with cases, t, the number of subjects who are cases in the INO-4800 group follows a binomial distribution with parameters (t, $p = \lambda_v/(\lambda_v + \lambda_c)$). The relationship between p and efficacy is: efficacy = (1-(1+k)p)/(1-p). Therefore, testing efficacy > 30% corresponds to testing p < 0.70/(0.70+k). Similarly, the confidence interval for efficacy is (1-(1+k)UB_p)/(1-UB_p), (1-(1+k)LB_p)/(1-LB_p), where UB and LB are the Clopper-Pearson upper and lower limits for the proportion.

The efficacy time frame is defined by symptoms beginning at any time starting from 14 days after Dose 2 and ending 12 months after Dose 2. Subjects identified as cases that started prior to this time point will be excluded. Subjects with multiple instances meeting the case definition will be counted only once, using the first such instance.

The PP population will be primary for the analysis of efficacy in this trial. Efficacy analysis using the mITT population will also be conducted counting cases from 14 days postdose 1 as a supportive analysis. The ITT population will also be used for a supportive analysis counting cases starting from randomization.

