8.6 SAMPLE SIZE/POWER

Phase 3 segment: The trial is case-driven. A total of 149 observed cases among baseline SARS-CoV-2 seronegative subjects will be required to provide 90% power to declare the vaccine efficacious (>30%), assuming a true efficacy of 60% and utilizing the methodology

INO-4800	COVID19-311
Inovio Pharmaceuticals, Inc.	Clinical Protocol

described in Section 8.5.1 and Section 8.5.6. A sample size of 6714 baseline SARS-CoV-2 seronegative subjects will be required to achieve this number of cases assuming an underlying attack rate of 3.7%.

8.7 **RANDOMIZATION AND BLINDING**

Phase 2 Segment

Subjects will be randomized (3 INO-4800 1.0 mg, one injection: 3 INO-4800 2.0 mg, two injections:1 Placebo, one injection: 1 Placebo, two injections).

The study is blinded. It is double-blinded within dose group. Randomization and blinding will avoid bias in the assignment of subjects to treatment, increase the likelihood that known and unknown subject attributes (e.g., demographics and other baseline characteristics) are evenly balanced between treatment groups, and enable valid statistical comparisons between treatment groups. Subject treatment assignments will be unblinded after Phase 2 subjects have reached the Week 30 visit.

Phase 3 Segment

Subjects will be randomized (2 INO-4800:1 Placebo). Randomization will be stratified according to two factors, each with two levels: a) age-group age category (18-50 years vs. ≥51 years) on Day 0, and b) presence or absence on Day 0 of underlying medical conditions that increase risk of severe COVID-19 disease, per US CDC criteria.

The study is double-blinded. Randomization and blinding will avoid bias in the assignment of subjects to treatment, increase the likelihood that known and unknown subject attributes (e.g., demographics and other baseline characteristics) are evenly balanced between treatment groups, and enable valid statistical comparisons between treatment groups.

9.0 **ETHICS**

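### Counting missing outcomes as COVID-19 cases biases the supportive Phase 3 ITT efficacy estimate: toward no effect if missingness is equal by arm, in either direction if it is not

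*Protocol*

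**What the plan says.** Section 8.5.8 opens with "Missing data will not be imputed". It then makes one exception: for the ITT analyses of efficacy in Phase 3, "subjects with missing or unevaluable data regarding case definition will be considered cases (failures".

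Section 8.4 defines ITT as everyone randomised and calls its analysis supportive of the per-protocol (PP) analysis. Section 8.5.1 adds: "The ITT population will also be used for a supportive analysis counting cases starting from randomization".

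Section 8.5.1 estimates efficacy from the split of cases between arms and from k, the ratio of placebo to vaccine follow-up time. A case's follow-up ends at first diagnosis; a non-case's ends at last follow-up.

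The rule is not left to another document. Section 8.1 states: "The formal Statistical Analysis Plan is contained in the sections that follow".

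**The concern.** Scoring a missing outcome as a failure is a familiar conservative device when failures are common. Here they are rare. An imputed case arises from a missing assessment, not from disease. If assessments go missing equally often in both arms, imputed cases fall 2:1 like the randomisation and carry a rate ratio of one. A small missing fraction is then enough to pull the estimate toward zero. If the arms differ in missingness, the estimate moves with that difference.

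The ITT analysis is the only efficacy analysis that keeps every randomised subject. PP removes subjects with incomplete dosing or protocol violations, and mITT removes the undosed. The purpose of ITT is to show whether those exclusions matter. A result driven by missing assessments cannot show that, and it could seem to disagree with a sound PP result.

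**Working it through.** **Inputs from the protocol**
- Section 8.6: 149 cases are "required to provide 90% power to declare the vaccine efficacious (>30%), assuming a true efficacy of 60" per cent; 6714 seronegative subjects are "required to achieve this number of cases assuming an underlying attack rate of 3.7" per cent.
- Section 8.7: "Subjects will be randomized (2 INO-4800:1 Placebo". The synopsis table gives 4476 vaccine and 2238 placebo seronegative subjects.
- No dropout or unevaluable rate is stated. The missing fraction m below is my assumption, shown as a range.

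**Reproducing the plan's case count.** Read 3.7% as the placebo attack rate over the endpoint window. The vaccine rate at 60% efficacy is 0.037 × 0.40 = 0.0148.

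2238 × 0.037 + 4476 × 0.0148 = 82.8 + 66.2 = 149.05 cases.

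This matches the stated 149 and equals 2.2% of 6714.

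**When imputed cases equal real ones.** Solve 6714m = (1 − m) × 149.05, so m = 149.05 / 6863.05 = 2.2%.

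**Effect of the rule, equal missingness.** With k = 2238/4476 = 0.5, the Section 8.5.1 formula reduces to one minus the ratio of arm risks:

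VE = 1 − [(1 − m) × 0.0148 + m] / [(1 − m) × 0.037 + m]

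At m = 5%: 1 − (0.01406 + 0.05) / (0.03515 + 0.05) = 1 − 0.06406/0.08515 = 25%.

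**Counting from randomisation.** Assume constant hazard and no protection until 14 days after dose 2 (Day 42). The endpoint window runs from Day 42 to Day 393, 351 days. The added risk in each arm is 0.037 × 42/351 = 0.0044, giving 0.0192 on vaccine and 0.0414 on placebo. With nothing missing, VE = 1 − 0.0192/0.0414 = 54%. The same formula with these risks gives the last column.

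| m (assumed) | Imputed cases, 6714m | Real cases left, 149.05(1 − m) | VE, endpoint window | VE, from randomisation |
|---|---|---|---|---|
| 0 | 0 | 149 | 60% | 54% |
| 1% | 67 | 148 | 47% | 43% |
| 2% | 134 | 146 | 39% | 36% |
| 5% | 336 | 142 | 25% | 24% |
| 10% | 671 | 134 | 15% | 15% |

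The real-case column counts the endpoint window only. Counting from randomisation adds about 6714 × 0.0044 ≈ 30 cases, which moves the break-even to 2.6% missing.

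**Unequal missingness** (endpoint-window risks, k = 0.5)
- True efficacy 60%, 12% missing on vaccine and 10% on placebo: 1 − (0.88 × 0.0148 + 0.12) / (0.90 × 0.037 + 0.10) = 1 − 0.1330/0.1333 ≈ 0%.
- True efficacy 0, 10% on vaccine and 15% on placebo: 1 − (0.90 × 0.037 + 0.10) / (0.85 × 0.037 + 0.15) = 1 − 0.1333/0.1815 ≈ 27%.

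The rule is therefore not reliably conservative.

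**Narrow reading.** Suppose the rule covers only suspected episodes with no evaluable RT-PCR, in a fraction q of each arm, added to the real cases.
- q = 0.5%: 1 − (0.0148 + 0.005) / (0.037 + 0.005) = 53%.
- q = 1%: 1 − 0.0248/0.047 = 47%.

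**Follow-up time.** An imputed case has no diagnosis date, so its contribution to k is unspecified. If missingness is equal by arm and one convention is applied to both, k stays near 0.5 and the table holds. If missingness differs, k depends on a convention the protocol does not give.

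**The case against.** The strongest reply rests on the qualifier in the rule: the data must be missing or unevaluable regarding the case definition. Section 8.5.1 already ends a non-case's follow-up at last contact. Read together, dropouts could be censored and only undetermined illness episodes imputed. The protocol also works to keep such episodes few, with an assessment visit and swab within 3 days, a local-laboratory fallback for hospitalised subjects, and EAC review. This reading is possible and gives a smaller bias. The text does not state it, however, and the bias does not vanish.

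Four stronger inferences are tempting and should not be drawn.
- **That imputed cases will swamp the real ones.** This needs more than about 2.2% to 2.6% missing on the broad reading, and the protocol gives no rate.
- **That Section 8.5.8 contradicts itself.** A general rule followed by a named exception is ordinary drafting.
- **That the analysis cannot be run.** What is missing is a date convention, which could be supplied.
- **That the trial's efficacy conclusion is at risk.** PP is primary, the success criteria belong to it, and no alpha or interim decision depends on ITT. The supportive mITT analysis, which keeps everyone dosed at least once, is not subject to this rule.

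Part of the fall from 60% also comes from counting from randomisation, not from this rule; hence the 54% baseline.

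The statistical text examined is that of versions 1.0USA and 2.0USA, which agree on this sentence. A version 7.0 page also appears, but its statistical section is not in the part available.

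**Conclusion.** The point holds as a moderate defect in a supportive analysis, not as something that must be fixed before the primary analysis can stand. On the plain reading, equal missingness of 1% to 10% takes expected ITT efficacy from about 54% to between 43% and 15%, or from 60% to between 47% and 15% if the early unprotected period is ignored. On the narrow reading, 0.5% to 1% of subjects with unevaluated episodes takes 60% to between 53% and 47%. Unequal missingness can bias the estimate in either direction.

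These figures rest on the plan's 3.7% placebo attack rate and 60% true efficacy, on missingness unrelated to disease risk, on k = 0.5, and on assumed missing rates. The 54% baseline further assumes constant hazard and no protection before 14 days after dose 2.

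**What to change.** Delete the missing-as-case sentence from Section 8.5.8. State that the ITT analysis counts only EAC-confirmed cases and censors non-cases at last follow-up, using the follow-up definition already in Section 8.5.1. This also removes the undefined follow-up time.

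Under non-informative loss the expected estimate is then unaffected by missingness. At 10% loss the endpoint-window case count would be about 149.05 × 0.90 = 134 if lost subjects contribute nothing, or 149.05 × 0.95 = 142 if they contribute half their follow-up.

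A tipping-point analysis for missing follow-up is optional. The cost is a short edit to the protocol text, with no new data and no burden on subjects. It should be made before unblinding so that it does not look post hoc.
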